## **Effectiveness of a multilevel integrated intervention for LDCT lung cancer screening and smoking cessation among African Americans**

### **Background**

African Americans have both the highest incidence and mortality of lung cancer compared to any other racial/ethnic group. A possible explanation for this disparity is that African Americans (AA) may be less likely to utilize preventative screenings such as low-dose computed tomography (LDCT), which has the potential to encourage smokers to quit smoking successfully. In 2021, the USPSTF expanded their lung cancer screening (LCS) recommendations to include individuals ages 50-80 years with at least a 20 pack-year history, increasing the number of eligible U.S. adults. While the expanded criteria are expected to increase the number of high-risk individuals eligible for screening and reduce lung cancer mortality, the impact on racial and ethnic minorities, including African Americans, has shown mixed findings. This is problematic as previous research has found that African Americans may have different quit behaviors than whites. While use of LCS as a teachable moment for tobacco cessation is important, currently, there is no well-integrated, comprehensive, culturally relevant community-engaged, sustainable program. Still, it is not clear whether the synergy effect of smoking cessation and LDCT LCS intervention was observed in both quitting behaviors and LDCT uptake among African American smokers. To address this urgent public health concern, this study aims to reduce disparities and the burden of lung cancer among AA smokers by supporting a Multiple-level intervention integrating lung cancer screening and smoking cessation (MILS), followed the NIH DEIA strategies using multilevel interventions that impact determinants of health and address health disparities at appropriate time points across the life course.

### **Significance**

In Louisiana, about 3,730 new lung cancers were expected to be diagnosed and about 2,620 patients were expected to die of lung cancer in 2016. In 2009-2013, Louisiana residents had the highest lung and bronchus cancer incidence rates compared with the U.S. national incidence

rates (75.3 vs 65.1 per 100,000). This incidence rate was even higher for African American males in Louisiana (110.6 per 100,000). Therefore, the immediate goals of this study are to expand understanding of the cognitive factors of TPB and develop an evidence-based intervention that targets at-risk African American smokers undergoing LDCT.

These aims directly align with the goals of both the National Cancer Institute (NCI) and PAR-23-122 and will increase knowledge of smoking cessation and LDCT LCS needs for African Americans in an effort to reduce the health burden of lung cancer. In addition, this study can also help build a robust screening program for the Louisiana Cancer Research Center (LCRC). It is not only beneficial for the LCRC population health program but will also reduce the burden of lung cancer within at-risk African American smokers undergoing LDCT. This work has great potential to help reduce the enormous public health burden of lung cancer and carry out the National Health Institute's mission by improving the health for medically underserved minority populations.

The results of our pilot test suggested that our intervention integrating smoking cessation and LDCT Lung cancer screening showed initial effectiveness in improving smoking cessation and knowledge and attitude toward LDCT screening. Yet it failed to address multiple-level Intervention and synergy effects among high-risk A.A. smokers. Beyond having sufficient knowledge about it, **multiple levels of Intervention integrating lung cancer screening and smoking cessation (MILS)** to increase LDCT uptake and quitting behaviors in racially and ethnically diverse populations are needed.

In summary, the proposed study is clinically relevant and significant for the following important reasons:

- It focuses on both smoking cessation and LDCT screening uptake, which are the two leading causes of Lung cancer prevention and control (reduce risk behaviors and earlier detection) in Louisiana.
- It addresses a hard-to-reach African American population in Louisiana, which is medically underserved and suffers from health disparities.

- It will result in the first MILS that can be used as an educational tool to facilitate patient education and increase LDCT understanding and uptake, which can lead to earlier detection and support for lung cancer prevention and control.
- Our MILS is an evidence-based, culturally, and linguistically appropriate multiple level intervention with significant potential to empower smoking cessation and LDCT screening, which is recommended by the U.S. Preventive Services Task Force and the American Cancer Society.
- MILS followed the NIH DEIA strategies, "Objective 3.2, Goal 2, Strategy 1: Design, adapt, test, and implement targeted, multilevel interventions that impact determinants of health and address health disparities at appropriate time points across the life course."
- With our promising pilot data, experienced team members and existing clinical sites (UMC), and newly added research team members with strong statistical and research skills, including community health workers who had a similar personal experience to our participants, our project has a high likelihood of success.

### Conceptual Framework

This proposed study using MILS, the development is based on the Social Ecological Model (SEM). The features and detailed information

of the MILS are stated in Table 3 on the following intersect:

#### 1. **Community Engagement (Diversity):**

MILS involve community engagement strategies that empower individuals and communities to actively participate in improving their health. Combining LDCT

screening and smoking cessation with community outreach and interactive social media

Table 3 Conceptual Framework

	MILS Intervention
Individual Level	
 
• Smoking cessation and LDCT LCS counseling guide by Theory
 
• Interaction between multiple levels levels
 

Healthcare provider Level	
 
• Provider training for smoking cessation counseling, assess eligibility for LDCT screening, and provide education about the process
 
• Efforts are made to ensure that access to both LDCT screening and smoking cessation programs is equitable and that individuals from diverse backgrounds have equal opportunities for participation
 

Community Level	
 
• Community Health Worker(CHW) trained to engage with the community, conduct outreach, and connect individuals to healthcare services, including LDCT screening and smoking cessation programs
 
• CHW bridge the gap between the community and healthcare system levels
 
• CHW tailored to the cultural, linguistic, and social nuances of the community, ensuring that messages and services resonate with diverse populations
 
• Interactive Social media(Facebook)
 

education can increase awareness of the importance of early cancer detection and encourage high-risk individuals to seek screening.

2. **Reducing Barriers to Access (Accessibility):** MILS focuses on removing barriers to accessing smoking cessation services or LDCT LCS, may face barriers related to cost, transportation, or awareness. A multilevel approach can address these barriers, making cessation service and LDCT screening more accessible to underserved populations.
3. **Tailored Education and Outreach (Inclusion/ Accessibility):** MILS recognizes the importance of tailoring education and outreach efforts to the unique needs and preferences of diverse communities. Integrating culturally sensitive and linguistically appropriate messaging into smoking cessation and LDCT screening can improve its acceptability and uptake among various populations.

**Equity in Healthcare (Equity):** Both smoking cessation and LDCT screening share the goal of achieving equity in healthcare. MILS aims to reduce health disparities, while smoking is a major risk factor for lung cancer, and LDCT screening contributes to early cancer detection, potentially reducing disparities in cancer outcomes. When used in conjunction, these approaches can address disparities from multiple angles.

### **Impact**

To date, no study has evaluated the synergy effect of smoking cessation intervention and LDCT LCS in African American populations with multilevel intervention strategies. We will move the field forward by providing effective, scalable interventions to improve both smoking cessation and LDCT lung cancer screening adherence to reduce health disparities promised by large clinical trials that motivated screening guidelines. This project will be a first step to exploring and addressing the smoking cessation needs of at-risk African American smokers undergoing lung cancer screening using the Theory of Planned Behavior to expand our understanding of the ideal teachable moment and content (barriers and facilitators) for a smoking cessation

intervention in a lung cancer screening context. An understanding of the cognitive factors associated with smoking cessation among at-risk African American smokers with provider and community engagement will help reduce disparities in lung cancer burden, including incidence and mortality. The proposed research is directly in line with NIH's mission to protect and improve health for medically underserved minority populations and the NIH DEIA strategies, design, adapt, test, and implement targeted, multilevel interventions that impact determinants of health and address health disparities at appropriate time points across the life course. This study prioritizes the examination of cancer and tobacco-related health disparities in underrepresented groups to ensure that findings inform equitable treatment and policy recommendations for everyone, regardless of age, race, income, geography, or sexual orientation. The results of the study will directly guide the development of targeted strategies to improve lung cancer screening rates among minorities.

### **Research Question**

We aim to answer the research question: **“How can disparities be rectified by expanding the diversity of individuals who receive screenings and ensuring equitable access to services?”** Answering this research question can help address the challenge of Black individuals experiencing lower success rates in quitting cigarette smoking than their white counterparts.

### **Research Objectives**

**Objective 1. Investigate smokers' and providers' attitudes, knowledge, and experiences with the expanded 2021 USPSTF Lung Cancer Screening (LCS) recommendations.** We will examine it using exploratory sequential mixed methods (integrating quantitative and Qualitative data). We will conduct focus groups for A.A. smokers who are eligible for LDC. Results will be used to expand the understanding of the needs and barriers of LDCT LCS and smoking cessation services to construct multiple levels intervention with the goal of increasing LDCT uptake and quitting behaviors.

**Objective 2. Compare the Effectiveness of a Multiple levels intervention integrating lung cancer screening and smoking cessation (MILS) vs. control group on the biochemically validated 7-day point-prevalence tobacco abstinence rates at 6 months, LDCT uptake, the change in tobacco consumption pattern, nicotine dependence and stage of change was assessed.** We will conduct a multiple level intervention integrating lung cancer screening and smoking cessation (MILS), including individual level: individual-based LDCT/smoking education (with Louisiana Tobacco Cessation Initiative); Institutional level: provider education (with university medical center); and community level: a community navigator (Community Health Worker) with interactive social media to increase LDCT uptake and quitting behaviors in racially and ethnically diverse populations. Multilevel intervention is a holistic approach to addressing health issues that recognize the complexity of health determinants. Multilevel interventions aim to change health behaviors and related outcomes by targeting multiple levels of influence, such as individuals, groups, organizations, and communities. Multilevel interventions can be delivered simultaneously or over time to achieve desired outcomes. For example, interventions integrating lung cancer screening and smoking cessation can work together synergistically to enhance early cancer detection and prevention.

LDCT is an evidence-supported lung cancer screening that is noted to increase early-stage lung cancer diagnosis. Early diagnosis can reduce lung cancer-related mortality and improve prognosis. **For this study, we are not directly providing lung cancer screenings. We are recruiting participants who are eligible for lung cancer screening and increase their knowledge, attitude, and intention to take LDCT.** We hypothesize that A.A. in the MILS group will achieve greater increases in LDCT uptake and quitting behaviors (e.g., biochemically validated 7-day point-prevalence tobacco abstinence rates at 6 months, the change in tobacco consumption pattern, nicotine dependence and stage of change) at post-treatment and follow-up than A.A. in the control group.

**Objective 3. Explore barriers and facilitators that influence primary outcomes at the community, provider, and individual levels for the improvement of a multilevel intervention (MILS).** We will conduct 30 qualitative key informant interviews (10 for each level) to identify barriers and facilitators that influence the adherence and implementation of MILS.

## **Methodology**

### **Study Design**

We used an exploratory sequential mixed method study design to culturally adapt the Smoking and LDCT Questionnaire and address the sociocultural contexts of smoking and LDCT LCS among African Americans. For Objective 1, thirty African American smokers eligible for LDCT LCS completed the qualitative interview/focus group. We integrated qualitative themes from the interview/focus groups were matched to survey domains (Objective 2) and some themes were used to develop a Multiple levels intervention integrating lung cancer screening and smoking cessation (MILS) intervention curriculum for a culturally adapted smoking cessation and LDCT LCS. For Objective 2, we will conduct a randomized control trial (RCT), which is a type of study that compares the effectiveness of different treatments or interventions by randomly dividing participants into groups, with a wait-list control design, which is when the control group serves as the untreated comparison group during the study, but eventually receives the treatment at a later date, to determine the Effectiveness of a Multiple levels intervention integrating lung cancer screening and smoking cessation (MILS) for African Americans undergoing LDCT. For Objective 3, we will conduct 30 qualitative key informant interviews (10 for each level) to identify barriers and facilitators that influence the adherence and implementation of MILS.

### **Study Sample/Recruitment**

Participants of the study will be recruited from the University Medical Center (UMC). Eligibility criteria will include: (1) self-identified as African American; (2) eligible for a LDCT (i.e., 50-77 years old; 20+ pack years of smoking) or have received a LDCT exam in the past; (3) current

smoker; and (4) English speaking. Eligible participants will be recruited from Tobacco Control Initiative (TCI) staff at UMC. Objective 1: Based on our previous qualitative studies, we anticipate reaching saturation after 30 in-depth interviews; however, we will consider increasing the number of interviews if needed. Objective 2: Two hundred fifty eligible A.A. smokers at UMC will be identified and recruited by TCI staff or UMC clinic and referred/enrolled to evaluate the Effectiveness of a Multiple levels intervention integrating lung cancer screening and smoking cessation (MILS) utilize a two-arm, parallel groups, randomized, controlled design. Objective 3: Ten participants, 10 providers and 10 community members will be asked to complete an in-depth interview.

### **Study Questionnaires/ Assessment Tools**

Primary outcomes were measured by survey before intervention, immediately after intervention, and 6-month after intervention. Outcomes include stage of change, 7-day PPA rate, 24-hour PPA rate, daily cigarette use, and the Fagerstrom Test for Nicotine Dependence score. Stage of Change was measured based on the TTM model. 7-day PPA at follow-up was measured with the question "Have you smoked any tobacco products in the last 7 days?" 24-hour PPA was measured using the question "Have you smoked any tobacco products in the last 24 hours?" Daily cigarette use was measured using a multiple-choice question with 4 answers: 1) 10 or less, 2) 11-20; 3) 21-30; or 4) 31 or more. The Fagerstrom Test for Nicotine Dependence was based on a 6-item validated questionnaire (Etter et al., 1999) Second, the LDCT uptake and intent to LCS constructs were measured by previously validated questionnaires. An additional amendment will be submitted for Year 2 measurements and aims. All surveys and questionnaires will be submitted in an amendment for Year 2 of the study, including all intervention materials.

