### **Data Analysis**

**Objective 1:** Qualitative data collected from semi-structure interviews, which is a research method that combines a set of predetermined questions with the ability for the interviewer to explore specific themes or responses. These interviews allow for a mix of predetermined questions and others that are not based on the participant's responses. The interviews will be transcribed, de-identified, and enter into Atlas.ti for data analysis. A thematic analysis will be conducted to understand participants' perspectives on smoking cessation and LDCT LCS. The primary analysis will be performed by two researchers independently. These two researchers will review the first 5 interviews to open code the data and to identify emergent themes. The multidisciplinary research team will then have meetings to discuss, operationalize, and refine the codes and themes to develop a coding scheme. The two researchers will use the developed coding scheme to independently code all the transcripts. They will have regular meetings to review coded transcripts together, identify and reconcile any coding discrepancies, and add newly merged codes and themes into the coding scheme. We will calculate the code frequencies to identify the most frequently mentioned points by participants under each theme. The final coding results will be reviewed and shared with all research team members for feedback and revision.

**Objective 2:** We plan to enroll a total of 250 participants (125 for each group; experiment and control group). Assuming a 20% attrition rate, we estimated 200 (100 per group) participants at the end of the study at the 6-month follow-up visit. A significant level of 0.05 is applied. We estimated that the biochemically validated 7-day point-prevalence tobacco abstinence rates at 6 months are 20-30% for the MILS group and 5% for the control group (Martha Andritsou et al., 2016). A sample size of 200 achieves 85.6-99.6% power to detect the group difference in tobacco abstinence rates at 6 months based on the two-sided Fisher's exact test. For the LDCT uptake, we estimate that the LDCT uptake at 6 months is 32-40% for the MILS group and 15% for the control group (Young PC et al., 2020; Coral Olazagasti et al., 2022). A sample size of 200 achieves 76.5-97.2% power to detect the group difference of the LDCT update based on the two-sided Fisher's exact test (Ryan, 2013).

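### The assessment section calls self-reported survey measures the primary outcomes, while Objective 2, the hypothesis and the power calculation use biochemically validated 7-day abstinence at 6 months

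*Protocol*

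**What the plan says.** Three parts of the protocol describe the outcomes of the randomised comparison, and they do not agree.

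- **Study Questionnaires/ Assessment Tools.** The opening sentence reads "Primary outcomes were measured by survey before intervention, immediately after intervention, and 6-month after intervention". The list follows: "Outcomes include stage of change, 7-day PPA rate, 24-hour PPA rate, daily cigarette use, and the Fagerstrom Test for Nicotine Dependence score". On abstinence it says "7-day PPA at follow-up was measured with the question" and gives one yes/no item on tobacco use in the past week; no biochemical test is mentioned. It then adds "Second, the LDCT uptake and intent to LCS constructs were measured by previously validated questionnaires", without saying whether these two are primary. The section also says that Year 2 measurements will come in an amendment.
- **Research Objectives, Objective 2.** The comparison is on "biochemically validated 7-day point-prevalence tobacco abstinence rates at 6 months, LDCT uptake, the change in tobacco consumption pattern, nicotine dependence and stage of change". The hypothesis under the same objective repeats the validated 6-month abstinence measure.
- **Data Analysis, Objective 2.** The sample size rests on two outcomes. The first is abstinence: "We estimated that the biochemically validated 7-day point-prevalence tobacco abstinence rates at 6 months are 20-30% for the MILS group", against 5% in the control group. The second is LDCT uptake at 6 months, 32-40% against 15%. A significance level of 0.05 is stated once.

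Participant Protections provides a $50 payment, for all participants, linked to biochemically verified abstinence at 6 months.

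**The concern.** The section that says how outcomes are measured gives a different primary smoking outcome from the sections that set the objective and the sample size. The author of an analysis plan could cite the first for self-report or the others for verified abstinence. The two can give different answers.

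Verification matters in this design. The control group is an untreated wait-list (Study Design), so participants can tell which arm they are in. Only MILS participants receive counselling, social media and community sessions, with payments for taking part (up to $300 against $150). Smokers who have been counselled to quit may claim abstinence more often than smokers who have not. An unverified outcome then shows a difference that is not there.

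The section also places five measures at two post-baseline times under the primary label and leaves LDCT uptake and screening intent without a status. So the protocol does not fix which measure, at which time, decides the trial.

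**Working it through.** **1. The passages side by side**

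| Place in protocol | Abstinence measure | Time | Other outcomes |
|---|---|---|---|
| Study Questionnaires/ Assessment Tools | one self-report item | post-intervention and 6 months | stage of change, 24-hour abstinence, daily cigarettes, Fagerstrom score; LDCT uptake and intent, status not given |
| Objective 2 | biochemically validated | 6 months | LDCT uptake, consumption, dependence, stage of change |
| Data Analysis | biochemically validated | 6 months | LDCT uptake (also powered) |
| Participant Protections | biochemically verified (payment) | 6 months | none |

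The payments show that verification is budgeted in both arms. Control: 50 + 50 + 50 = $150. MILS: 150 + 50 + 40 + 60 = $300. Both totals match the protocol and both contain the verification payment.

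**2. The stated power**

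Inputs from Data Analysis: 250 enrolled, 20% attrition, so 250 × 0.8 = 200, or 100 per arm; two-sided 0.05. The stated figures follow from the continuity-corrected normal approximation:

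power = Φ{ [|p1 − p2| − 1/n − 1.96 √(2p̄(1 − p̄)/n)] / √[(p1(1 − p1) + p2(1 − p2))/n] }

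For 20% against 5%: p̄ = 0.125 and n = 100, so (0.15 − 0.01 − 1.96 × 0.04677)/0.04555 = 1.061, and Φ(1.061) = 85.6%. The other three cases give 99.6%, 76.5% and 97.2%. All four match the protocol. Exact Fisher enumeration gives 88.3%, 99.8%, 77.2% and 97.4%. The stated power is therefore sound for validated abstinence and for LDCT uptake. No power is given for the self-reported version or for the other listed measures.

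**3. What self-report could do to the false-positive rate**

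Assumptions: true abstinence is 5% in both arms (the protocol's control rate), with 100 per arm. A fraction f of continuing smokers reports abstinence. The misreporting fractions are not in the protocol, so a range is shown. The reported rate in an arm is 0.05 + 0.95 f. The last column sums the exact binomial probabilities of all tables that the two-sided Fisher test rejects at 0.05.

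| f in MILS | f in control | Reported, MILS | Reported, control | False-positive rate |
|---|---|---|---|---|
| 0 | 0 | 5.0% | 5.0% | 2.1% |
| 5% | 5% | 9.75% | 9.75% | 2.8% |
| 5% | 2.5% | 9.75% | 7.375% | 5.6% |
| 10% | 5% | 14.5% | 9.75% | 12.9% |
| 5% | 0 | 9.75% | 5.0% | 17.4% |
| 10% | 0 | 14.5% | 5.0% | 54.6% |

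The harm comes from the difference between arms. Equal misreporting at 5% barely moves the error.

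**The case against.** Three objections carry weight.

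- **Verification is clearly intended.** It appears in the objective, the hypothesis, the power assumption and the payments in both arms. The assessment section describes questionnaires, and a 7-day question is the usual first step of validated abstinence. The section also announces an amendment for Year 2 measurements. This stands. A reader might infer that the trial's main result will be unverified, but the documents do not support that. They leave open which version is primary.
- **Multiplicity may be handled elsewhere.** A reader might infer many tests, each at 0.05, with a familywise error of 9.75% for the two powered outcomes (1 − 0.95²) or more for the longer list. The protocol states 0.05 once and does not say that every listed item is a success test. A rule may sit in an analysis plan that is not at hand. The 9.75% also assumes independent tests at full size. The exact Fisher sizes at the protocol's control rates are 2.1% (5% against 5%) and 3.3% (15% against 15%), so even under independence the joint figure is 1 − 0.979 × 0.967, about 5.3%. No finding on familywise error is made here.
- **The worst misreporting cases are severe.** The 17.4% and 54.6% rates need no false reports at all among controls. The MILS payments reward attendance and social media use, not a claim to have quit. This is fair; the milder rows are the more cautious guide.

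None of this removes the conflict over which abstinence measure is primary. That choice belongs in the protocol, and here the protocol gives two answers.

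**Conclusion.** The inconsistency is real and should be corrected. The assessment section gives the primary label to survey measures and defines 7-day abstinence by self-report. The objective, hypothesis and sample size use the validated 6-month measure. If the assessment section were followed, the false-positive rate for abstinence would rise from 2.1% to between 5.6% and 54.6% over the unequal misreporting scenarios shown. Those figures assume 5% true abstinence in both arms, 100 analysed per arm and misreporting rates chosen for illustration.

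It would be tempting to add that the objective and power rest on a single validated outcome. They do not: Objective 2 names several outcomes, and the sample size section also powers LDCT uptake at 76.5-97.2%. What is missing is a consistent statement of the primary outcome or outcomes, with time point and verification rule.

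**What to change.** Amend Study Questionnaires/ Assessment Tools; the Year 2 amendment that the section announces is the natural place, before any Aim 2 outcome data are seen.

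1. Define the primary smoking outcome as self-reported 7-day abstinence confirmed by the biochemical test at 6 months, and name the test and the rule for confirmation.
2. Make unverified 7-day and 24-hour abstinence, stage of change, daily cigarettes, Fagerstrom score and all immediate post-intervention results secondary.
3. State whether LDCT uptake at 6 months is a second primary or a key secondary outcome, and give screening intent a status. If LDCT uptake is a second primary, say how 0.05 is shared.

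The third choice is the sponsor's, because the trial treats cessation and screening as joint aims:

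- **Fixed sequence, abstinence first.** Abstinence power stays at 85.6-99.6%. At the lower assumed effects, and if the two tests are independent, the chance of a formal LDCT claim falls from 76.5% to 0.765 × 0.856 = 65%. It is near zero if MILS affects screening only.
- **Equal split, 0.025 each.** By the formula that reproduces the stated power, abstinence has 78.0-99.1% and LDCT uptake 66.9-94.8%.

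The cost is protocol wording. No participants are added, and the verification payments are already budgeted in both arms.

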### **Participant Protections**

All participants' privacy will be fully protected by the research team during the study. (\$100 per participant for Aim1 & Aim 3, \$150-300 per participant for Aim 2; Aim 2 conducted in year 2 and 3). All participants received payment for completing a baseline assessment (\$50) and follow-up assessment (\$50) and a biochemically verified abstinence at the 6-month assessment (\$50). Intervention group participants also received compensation for attending counseling (\$50) or accessing social media (\$40) and for at least two community section (\$60). Intervention group participants could receive up to \$300 in incentive payments. Control participants could receive up to \$150.

Each participant will receive an oral and written explanation of the purpose, procedure, and risks of the study before participating in the research study. Verbal consent will be obtained prior to any data collection and before participating in the research study. The principal investigator and sub-investigators will be available to answer all questions before and after the study is conducted. The greatest risk in the study, which is minimal and low risk, is a breach of confidentiality. The study is focused on a non-sensitive topic, and the participants are not at risk for mental or emotional reactions. There may be no direct benefit to participants participating in the study.

Approval to conduct this study will be obtained prior to conducting the study through the LSUHSC-NO IRB.

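### The powered endpoint is tobacco abstinence, but its survey items ask only about smoking, and the tobacco-consumption outcome is recorded only in cigarettes

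*Protocol*

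**What the plan says.** Research Objectives (Objective 2) lists the outcomes as "biochemically validated 7-day point-prevalence tobacco abstinence rates at 6 months, LDCT uptake, the change in tobacco consumption pattern, nicotine dependence"; stage of change is listed too. Data Analysis (Objective 2) powers the first of these, assuming that "biochemically validated 7-day point-prevalence tobacco abstinence rates at 6 months are 20-30% for the MILS group and 5% for the control group".

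Study Questionnaires/ Assessment Tools gives the items. Seven-day abstinence is asked as "Have you smoked any tobacco products in the last 7 days" and 24-hour abstinence as "Have you smoked any tobacco products in the last 24 hours". Consumption is described as follows: "Daily cigarette use was measured using a multiple-choice question with 4 answers: 1) 10 or less, 2) 11-20; 3) 21-30; or 4) 31 or more". Participants are surveyed, in that same section, before the intervention, immediately after it and 6 months after it, and the full set of surveys is deferred to a Year 2 amendment.

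Verification appears in the objective, in the power statement and in Participant Protections, which attaches a payment to "a biochemically verified abstinence at the 6-month assessment". None of these places names the marker or its cut-off. Study Sample/Recruitment requires a current smoker and does not say of which product.

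**The concern.** The endpoint is named for one construct and asked about in terms of another. Tobacco abstinence covers every tobacco product; the item covers only tobacco that is smoked. Someone who has left cigarettes for smokeless tobacco is not tobacco-abstinent, yet answers no truthfully. Someone who vapes could answer either way, depending on how they read the question.

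If verification does not catch these participants, a smoke-free rate would be reported as a tobacco-abstinence rate. Any difference between arms in moving to other products would then enter the treatment comparison. Such a difference is plausible, because one arm is counselled to quit and the other waits, but the document gives no rate for either arm.

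The consumption outcome has a related gap. The objective speaks of tobacco and the item counts cigarettes.

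**Working it through.** **1. The plan's own power figures.** Inputs from Data Analysis: 100 evaluable per arm (250 × 0.8 = 200), two-sided 5% level, 20–30% vs 5%. The stated power is 85.6–99.6%. The continuity-corrected two-proportion formula, solved for power at n = 100 with d = p₁ − p₂ and p̄ the mean rate, is

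z = {d·[√n − 1/(d√n)] − 1.96·√(2p̄(1−p̄))} / √(p₁(1−p₁) + p₂(1−p₂))

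- 20% vs 5%: (0.15 × 9.333 − 1.96 × 0.4677) / 0.4555 = 1.06, so power is 85.6%.
- 30% vs 5%: (0.25 × 9.6 − 1.96 × 0.5374) / 0.5074 = 2.65, so power is 99.6%.

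Both stated figures reproduce. Full enumeration of the two-sided Fisher test gives 88.2% and 99.8%, so the stated values are slightly conservative. The point here concerns what is measured and leaves these figures intact.

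**2. How each kind of user would be scored at 6 months.** The protocol does not name the marker, so two generic types are assumed: one that detects nicotine exposure and one that detects smoke exposure.

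| Product used after cigarettes | Truthful answer to the 7-day item | If nicotine-based marker | If smoke-based marker |
|---|---|---|---|
| Cigars, pipe | Yes | Failure already | Failure already |
| Unsmoked tobacco | No | Scored as failure | Scored as abstinent |
| E-cigarette with nicotine | Unclear | Scored as failure | Abstinent if the answer is no |
| Nicotine replacement only | No | Scored as failure | Scored as abstinent |

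Only rows two and three carry the mismatch in the question. Row two goes wrong under a smoke-based marker. Under a nicotine-based marker row two is right for tobacco abstinence, but row four goes wrong, because a person using no tobacco is failed. The direction of error therefore turns on an unstated choice. At the survey immediately after the intervention no verification is described, so abstinence there appears to rest on the item alone.

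**3. Illustration of size.** The document gives no rate of product switching. Every rate here is assumed, and verification is assumed to miss every switcher. Power is for the two-sided Fisher test with 100 per arm.

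| Assumed switching | True tobacco-abstinence rates | Chance of significance at those rates |
|---|---|---|
| None | 20% vs 5% | 88.2% |
| 10% of scored abstainers, both arms | 18% vs 4.5% | 83.4% |
| 20% of scored abstainers, both arms | 16% vs 4% | 77.4% |
| 2 points, MILS only | 18% vs 5% | 79.1% |
| 5 points, MILS only | 15% vs 5% | 58.6% |

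At 30% vs 5%, a 20% share in both arms still leaves 98.7%. If there were no true effect (5% in both arms), undetected switching in MILS alone would give a significant result with probability 5.0% at 2 points and 19.0% at 5 points, against 2.1% with none. At the low end these effects are small.

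**4. Consumption.** The objective promises "the change in tobacco consumption pattern, nicotine dependence and stage of change was assessed", but the only consumption item is daily cigarettes in four bands. A participant who goes from 11–20 cigarettes a day to cigars or smokeless tobacco falls into the band of 10 or less and shows a reduction. A participant already in the lowest band shows no change. The item feeds a separate outcome and plays no part in the powered comparison.

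**The case against.** The strongest reply has four parts.

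- *The item already covers much of the ground.* It asks about smoking any tobacco product, so a change from cigarettes to cigars or a pipe is scored as failure. This is right. A reader might infer that switching product in general counts as success on the powered endpoint; the wording of the item rules that out.
- *The powered endpoint is not the item alone.* It also requires biochemical verification, which may catch unsmoked tobacco. This stands as a limit on the claim. It does not remove the mismatch, because the marker is unnamed and one plausible type would not detect unsmoked tobacco.
- *Not smoking is a coherent target for a trial of smoking cessation and lung screening, so the word tobacco may simply be loose.* That is a fair reading, and choosing smoking abstinence would be legitimate. The protocol nevertheless names tobacco abstinence in the objective, the hypothesis and the power statement, so the name and the items need to agree.
- *The surveys are not final.* True, and for that reason the change is cheap. The wording of the abstinence items is, however, already fixed in the protocol text.

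A reader might also infer an inflated effect, for example 5 points of a planned 15, or a third. That pairs the worst assumed switching with the smallest planned difference and assumes that verification misses everyone. Nothing in the document supports those inputs, or shows that MILS raises switching.

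**Conclusion.** Two mismatches stand on the protocol's own words. The tobacco-abstinence endpoint rests on items that ask about smoking, which lets unsmoked tobacco through and leaves vaping undefined. The tobacco-consumption outcome is measured in cigarettes only, which is a separate matter and does not affect the powered endpoint.

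The size and direction of any error in the abstinence comparison cannot be established: they depend on an unnamed marker and on switching rates that the document does not give. The figures above show what could happen under assumptions and are not estimates. The stated power is not in error. The point is worth acting on because the remedy is small and because product use not recorded at 6 months cannot be reliably recovered later.

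**What to change.** Make these changes in the survey amendment already planned for Year 2:

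- Reword the 7-day and 24-hour items to ask whether the participant has *smoked or used any tobacco product*, with a tick box for each of cigarettes, cigars, pipe and smokeless tobacco, and separate boxes for e-cigarettes and nicotine replacement.
- Score the named tobacco-abstinence endpoint from all tobacco products and report smoke-free status alongside it.
- State in advance how vaping alone is classified. Either choice can be defended; it should be made before data are seen.
- Read the biochemical result against the reported products, so that nicotine replacement alone is not scored as tobacco use.
- Either record the amount used of other tobacco products, or rename the consumption outcome *daily cigarette use*.

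The cost is a few items, about a minute more per survey, and possibly a slightly lower abstinence rate than under the smoking-only question.
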